## GENERAL INFORMATION

Clinical Study Proposal	
Study Design	Sponsored Study, Prospective, single-center, randomized
Title - Acronym	Robotically assisted PCI in ostial lesions: the ROB-OSTIAL study
Sponsor	Corindus, Inc. dba Siemens Healthineers Endovascular Robotics
Funding address	[name]
Primary Investigator (PI)	[name] MD
Institution	Maria Cecilia Hospital – GVM Care and Research Cotignola (IT)
Version	A
Projected Dates of Study	Estimated First patient in: February 2023 Expected Time to Complete Enrollment: August 2024 (18 months) Expected Time of each Subject to Complete the Study: 1 month Total Expected Duration of the Study: 21 months Estimated study end: November 2024
GCP Statement	The study will be conducted in accordance with the ethical principles that have their origin in the Declaration of Helsinki and are consistent with ICH Good Clinical Practice as well as regulatory requirements
Confidential	This protocol is the property of the Sponsor and may not – in full or in part – be passed on, reproduced, published or otherwise used without permission

\* ICH: The International Council for Harmonisation of Technical Requirements for Pharmaceuticals for Human Use

[figure not shown]
## SYNOPSIS

Research Topic:	Robotically assisted PCI in ostial lesions: the ROB-OSTIAL study
Summary of Proposal:	
To assess accuracy of robotic-assisted PCI in obtaining full ostial lesion coverage and minimal protrusion compared to manual PCI.
 
Robotically assisted PCI offers the opportunity of performing minimal device movements (up to a minimum of 1 mm) in a stable and reproducible setting. This feature may be of great help when dealing with ostial lesions, whose treatment requires a precise stent positioning to avoid strut protrusion but also geographic miss of the lesion. Robotic-assisted PCI for ostial lesions showed encouraging results in large observational registries, but no study compared this approach with manual PCI.
 
We aim to perform a randomized (1:1) study comparing manual (n=33) and robotic-assisted PCI (n=33) in obtaining full lesion coverage when treating ostial lesions (ostial left main will be excluded).
 
Primary endpoint of the study will be full ostial coverage as assessed by IVUS imaging, while secondary endpoints will be procedural success, vessel damage and number of protruding struts in the donor vessel as assessed by IVUS imaging.

Summary of Timeline:	Starting in 2023 (after EC approval), approximate duration 21 months

**STUDY TABLE OF ASSESSMENTS**

Assessment	Enrollment	Procedure	Discharge	1M FU (± 7 days)
Eligibility criteria	X	X		
Informed consent	X			
Medical and Cardiac history	X			
Canadian Cardiovascular Society (CCS) Angina Grade	X		X	X
Hemoglobin/hematocrit	X			X
CK and/or CK-MB and troponin	X		X	
Total Cholesterol	X			X
Creatinine and Glomerular filtration rate	X		X	X
12-lead ECG	X		X	X
Concomitant Therapy	X		X	X
Procedure: Coronary angiography		X		
Procedure: Percutaneous Coronary Intervention (PCI)		X		
Procedure: Intravascular Ultrasound (IVUS)		X		
MACE - MAE			X	X
Adverse event		X	X	X

**STUDY FLOW CHART**

## 1. RATIONALE

Robotic PCI is known to reduce geographical miss of coronary lesions and increase accuracy of stent placement during coronary PCI. Its role may be particularly helpful when treating ostial lesions, which require a precise stent positioning in order to reduce long-term clinical events.

### 1.1 Clinical need

Accurate placement of coronary stents in ostial locations is known to be challenging (1). Angiographic ostial location ambiguity, often requiring multiple views, and problems with the motion of the stent before deployment are considered possible relevant sources of mistakes during PCI (2). Advancement of the stent past the ostium can lead to "geographic miss" where suboptimal scaffolding of the plaque or lack of coverage of areas exposed to balloon injury increase the risk of restenosis (3-5). If the stent is protruding in the donor vessel, it may cause difficulties, including 1) The need to re-cannulate the coronary artery, 2) a possible re-wiring through the side of the stent (in case of re-intervention) with subsequent stent deformation, and 3) unopposed struts undergoing an irregular process of endothelialization and neointima coverage (6,7). Of note, a retrospective analysis of 100 consecutive PCI of aorto-ostial lesions observed stent misplacement (defined as a stent deployed > 1 mm from the ostium) in 54% of cases, of which proximal and distal misses were equally represented (8). Interestingly, a geographic miss was associated with higher rates of restenosis and target lesion revascularization (TLR) compared with 'accurate' stent placement.

The use of robotic PCI is able to offer some advantages compared to manual PCI, including the reduction of longitudinal 'geographic miss' and the possibility of performing 1-mm accommodations in device positioning. In addition, it can improve lesion length evaluation as previously reported (9). The adjunct role of robotic-PCI in improving lesion coverage during ostial vessels PCI has never been previously evaluated.

## 1.2 Device Description

The CorPath® GRX System is intended for use in the remote delivery and manipulation of coronary or peripheral guidewires, rapid exchange (RX) devices and guide catheters during percutaneous coronary intervention (PCI) procedures.

The complete CorPath GRX System includes the following major components:

**The Bedside Components** consist of an Extended Reach Arm, Robotic Drive and Single-use Cassette. The Extended Reach Arm is mounted on a bed rail and supports the Robotic Drive.

- **Robotic Drive:** Receives inputs from the Control Console. These inputs actuate mechanical operations in Single-use Cassette as movements to a loaded guidewire, RX device, and guide catheter. The Robotic Drive moves forward and backwards to advance and retract the guide catheter. A Bedside Touchscreen on the Robotic Drive provides the user interface for bedside operator during system set-up, loading and device exchanges.
- **Single-use Cassette:** Attaches to the Robotic Drive and can be loaded with commercially available guide catheters, guidewires, and RX devices. This

Single-use Cassette advances, retracts, and rotates the guidewire, advances and retracts the RX device, and rotates the guide catheter.

- **Extended Reach Arm:** Mounted on the rail of the procedure table and supports the Robotic Drive.

**The Interventional Cockpit** houses the Control Console, the X-ray Foot Pedal, and Monitor(s) to display angiographic and hemodynamic data. It is designed to protect the physician from radiation exposure while maneuvering interventional devices.

**Control Console:** The Control Console enables the physician to remotely manipulate the guide catheter, guidewire, and RX device. The Control Console has a touchscreen and three joysticks: one joystick for RX device manipulation, one for guidewire manipulation, and a third joystick for guide catheter manipulation.

## 2 STUDY DESCRIPTION

This is Sponsored, prospective, single-center, randomized study. Subjects who meet eligibility criteria are randomly assigned (1:1) to manual PCI (n=33) or robotically-assisted PCI (n=33). In both arms, the final result will be evaluated by IVUS assessment of ostial coverage.

### 2.1 Endpoints

The aim of this study is to (1) compare ostial coverage and (2) strut protrusion, as assessed by IVUS, between a strategy of robotic-PCI and a strategy of standard

manual PCI in a prospective randomized study including subjects undergoing elective PCI at a single high-volume center.

**Primary endpoints:**

- 1) Evidence of full ostial coverage at angiographic and IVUS assessment

**Secondary endpoints:**

- 1) Distance from most proximal stent strut and coronary ostium (mm), as assessed by IVUS
- 2) In-hospital major cardiovascular events
- 3) Procedural duration (defined as the duration from when the sheath is inserted until it is removed)
- 4) Major adverse cardiovascular events at 1 month follow-up

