### **5 DESCRIPTION OF CLINICAL INVESTIGATION RELATED PROCEDURES**

#### **5.1 Baseline evaluation, subject enrollment**

All patients admitted and evaluated for coronary angiography and potential PCI will be screened at hospital admission for study eligibility by a member of the investigational site's research team that will review the patient's medical history.

At this point and prior to undergoing any study-related procedures, the informed consent must be explained and signed. During the consent discussion, the investigator or his/her designee must fully illustrate all pertinent aspects and risks of the study and related procedures. In particular, the subject must be informed that randomization will only be done after coronary angiography and coronary lesion suitability assessment. No additional procedure will be performed to assess lesion suitability, as the ostial disease will be only defined by angiography. The subject will be considered enrolled after the coronary angiography is complete and the subject is randomized.

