## **5.3 Coronary angiography**

After a written informed consent form has been obtained, the subject will undergo coronary angiography. If the presence of critical coronary lesions eligible for PCI is confirmed, lesion-related inclusion/exclusion criteria will be checked to go to the next step of randomization.

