#### **5.4 Randomization**

Once the investigator has determined that the subject and the procedure are eligible based on inclusion/exclusion criteria, the subject will be randomized in a 1:1 fashion to either robotic-assisted PCI or conventional manual PCI. Randomization is completed after the primary operator assesses the coronary lesion(s). Qualified subjects will be randomized to treatment using an Interactive Web-based Randomization System (IWRS). The IWRS will assign treatment arm and will be recorded in the CRF.

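### Procedural duration is timed from sheath insertion but assignment comes after angiography, so the comparison probably carries pre-assignment time that costs some precision without causing bias

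*Combined protocol and SAP*

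**What the plan says.** Secondary endpoint 3 (section 2.1) is "Procedural duration (defined as the duration from when the sheath is inserted until it is removed". Both landmarks are objective and the definition is clear for a single procedure.

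Assignment comes later than the first landmark. Section 5.1 says that "randomization will only be done after coronary angiography and coronary lesion suitability assessment". Section 5.3 adds that, once angiography confirms a treatable lesion, "lesion-related inclusion/exclusion criteria will be checked to go to the next step of randomization". Section 5.4 repeats the order and has the arm assigned through an IWRS and entered in the CRF.

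Whether PCI follows at once is not stated. Section 5.1 says that "All patients admitted and evaluated for coronary angiography and potential PCI will be screened at hospital admission", and the Study Table of Assessments lists "Procedure: Coronary angiography", PCI and IVUS under one procedure visit, with no staged visit. Section 2.1 describes "subjects undergoing elective PCI at a single high-volume center", which fits either arrangement.

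Section 3 gives a sample size for geographic miss only. The documents give no SD, expected difference, power or analysis method for duration, and they do not mention recording the time of assignment.

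**The concern.** If angiography and PCI share a session, the measured interval has two parts: time before assignment (diagnostic images, eligibility check, IWRS call) and time after it. Only the second can differ because of the assigned method. The first adds variation between subjects but no treatment effect.

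The stake is the width of the confidence interval for the between-arm difference in duration, with 33 subjects per arm. Unless the assignment time is kept, the two parts may not be separable at analysis.

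**Working it through.** **The plan's own figure.** Section 3 gives 66 subjects for a fall in geographic miss from 0.50 to 0.50 × (1 − 0.70) = 0.15, at 5% significance and 80% power. The two-sided two-proportion formula gives 27 per arm without continuity correction and 33 per arm with it, so 66 is reproduced. That figure concerns the primary endpoint and has no bearing on duration.

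**Inputs for duration.** From section 3: 33 per arm. Assumed, because the documents give neither: r, the SD of pre-assignment time divided by the SD of post-assignment time, and ρ, the correlation between the two. The unit below is the SD of post-assignment time.

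**Bias.** Pre-assignment time is fixed before the arm is known, so its expected value is the same in both arms. It cancels from the mean difference in minutes. A ratio or percentage difference would be diluted, because the common time enters the denominator.

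**Precision, unadjusted.** Var(pre + post) = 1 + r² + 2ρr, so the standard error relative to a clock started at assignment is √(1 + r² + 2ρr). At ρ = 0:
- r = 0.25: √1.0625 = 1.031, a rise of 3%.
- r = 0.5: √1.25 = 1.118, a rise of 12%.

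The ratio is below 1 when r² + 2ρr < 0, that is ρ < −r/2. The break-even correlations are −0.125 and −0.25.

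**On the confidence interval.** With the clock started at assignment, the 95% half-width is t(0.975, 64 df) × √(2/33) = 1.998 × 0.2462 = 0.492 SD. At ρ = 0 it becomes 0.492 × 1.031 = 0.507 SD or 0.492 × 1.118 = 0.550 SD.

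**Precision, adjusted.** Regressing sheath-to-sheath time on arm and pre-assignment time leaves a residual variance of 1 − ρ². Estimating one slope costs a factor √(1 + 1/62) = 1.008. The standard error relative to the assignment clock is therefore 1.008 × √(1 − ρ²), whatever r is.

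| ρ | r | Unadjusted | Adjusted | Adjusted ÷ unadjusted |
|---|---|---|---|---|
| 0 | 0.25 | 1.031 | 1.008 | 0.98 |
| 0 | 0.5 | 1.118 | 1.008 | 0.90 |
| +0.3 | 0.25 | 1.101 | 0.962 | 0.87 |
| +0.3 | 0.5 | 1.245 | 0.962 | 0.77 |
| −0.3 | 0.25 | 0.955 | 0.962 | 1.01 |
| −0.3 | 0.5 | 0.975 | 0.962 | 0.99 |

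**Worst case of adjusting.** (1 + r² + 2ρr) − (1 − ρ²) = (r + ρ)², which is never negative. So, apart from the 0.8% for the slope, adjustment cannot be less precise than the unadjusted comparison.

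**The case against.** The other side has a good deal in its favour.

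- **No defect in validity.** Sheath-to-sheath time is clearly defined and a legitimate measure, and its mean difference is unbiased. This stands, and is why the endpoint should be kept.
- **The premise is conditional.** If PCI is staged with a new sheath, the precision point falls away. This stands, although the plan would then need to say which sheath insertion starts the clock.
- **The size is assumed.** Neither r nor ρ is in the documents, and a sufficiently negative correlation turns the loss into a small gain. This stands. A reader might take r = 1.0, where the standard error rises by 41% and 80% power falls to 51%. Nothing in the documents supports diagnostic time as variable as the whole intervention, and the plan sets no power target for duration.
- **The time may exist already.** A reader might infer that assignment time is not captured. Section 5.4 says the assignment is recorded in the CRF, and the CRF fields and IWRS specification are not in the documents. All that can be said is that the protocol does not mention recording the time.
- **Moving the clock has its own risk.** Limiting the main comparison to subjects whose PCI was in the same session could select differently by arm, because deferral may be decided after assignment. This stands, and that restriction should not be adopted.
- **Other time remains.** Section 5.6 lets non-target lesions in either arm be treated by either method. That time stays in the interval under any of these options.

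**Conclusion.** The point holds as a minor improvement to a secondary endpoint. If PCI follows angiography in the same session, as the assessment table suggests, the duration comparison carries time that the assigned method cannot affect, and precision is likely somewhat reduced. With zero correlation and r between 0.25 and 0.5, both assumptions, the standard error is about 3% to 12% larger. A positive correlation makes the loss larger, and a correlation below −r/2 removes it.

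A reader might go further and infer that the duration result is biased or that the trial's power is compromised. The documents support neither: time before assignment is balanced in expectation, and the primary endpoint and the total of 66 do not depend on duration.

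**What to change.** 1. State whether PCI follows angiography in the same session and, if it can be staged, which sheath insertion starts the clock.
2. Record the IWRS assignment time in the eCRF.
3. Keep sheath-to-sheath time as the endpoint for all randomized subjects, and report the difference in minutes.
4. Pre-specify that the between-arm comparison is adjusted for the time from sheath insertion at angiography to assignment. This covariate is fixed before assignment for every subject.
5. Time from assignment to sheath removal may be reported as a separately named supportive measure. Do not restrict the main comparison to same-session PCI.

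The cost is one extra time stamp and one degree of freedom, at most about 1% in standard error. The adjustment recovers the loss most fully when nearly all PCI is in the same session. It does not remove time spent on non-target lesions.

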**2.2 Inclusion criteria**

1. Male or nonpregnant female aged  $\geq 18$  years
2. Coronary ostial lesions suitable for percutaneous coronary intervention (PCI).
3. The subject has been informed of the nature of the study, agrees to its provisions and has provided written informed consent.

## 2.3 Exclusion criteria

### Subject relevant criteria

1. Cardiogenic shock or hemodynamic instability requiring support.
2. ST-elevation myocardial infarction.
3. Ongoing acute renal failure.
4. In the opinion of the investigator, the subject is deemed unsuitable for robotic PCI due to clinical status and/or anatomic characteristics

### Lesion relevant criteria

5. Ostial left main disease
6. Chronic Total Occlusion

## 2.4 Risks and benefits

Indications to PCI, PCI itself, and medical management of subjects will follow scientific evidence and guidelines. Robotically-assisted PCI did not show safety concerns in published studies and is currently conceived as an adjunctive tool to improve PCI accuracy. The potential benefits of robotically-assisted PCI in this specific setting include a better procedural result (IVUS evidence of full ostium coverage with no/minimal protrusion in the donor vessel) with no difference in major short-term outcomes.

All materials employed are currently commercially available and CE marked.

### **3 STATISTICAL DESIGN**

The present study is a prospective, randomized 1:1, single-center study. It is intended for subjects with indications of coronary revascularization and coronary lesions suitable for PCI. Subjects will be randomly assigned to one arm out of two: robotic PCI (n=33) or manual PCI (n=33) in a 1:1 ratio.

Based on previous studies, we estimated an overall incidence of geographic ostial miss of 50%. Assuming that the use of robotic PCI can selectively achieve at least a 70% reduction of the geographic miss, 66 subjects are required to have an 80% chance of detecting, as significant at the 5% level, a 70% decrease of geographic miss from manual PCI to robotic PCI arm.

### **4 METHODS FOR ASSESSING AND RECORDING DATA**

Data will be recorded on individual subjects' case report forms (CRF) within the electronic data capture (EDC) system.

### **5 DESCRIPTION OF CLINICAL INVESTIGATION RELATED PROCEDURES**

#### **5.1 Baseline evaluation, subject enrollment**

All patients admitted and evaluated for coronary angiography and potential PCI will be screened at hospital admission for study eligibility by a member of the investigational site's research team that will review the patient's medical history.

At this point and prior to undergoing any study-related procedures, the informed consent must be explained and signed. During the consent discussion, the investigator or his/her designee must fully illustrate all pertinent aspects and risks of the study and related procedures. In particular, the subject must be informed that randomization will only be done after coronary angiography and coronary lesion suitability assessment. No additional procedure will be performed to assess lesion suitability, as the ostial disease will be only defined by angiography. The subject will be considered enrolled after the coronary angiography is complete and the subject is randomized.

## **5.2 Screen Failure**

A subject who signs an informed consent form (ICF) and does not undergo randomization will be considered a screen failure and should be treated according to the standard of care.

## **5.3 Coronary angiography**

After a written informed consent form has been obtained, the subject will undergo coronary angiography. If the presence of critical coronary lesions eligible for PCI is confirmed, lesion-related inclusion/exclusion criteria will be checked to go to the next step of randomization.

#### **5.4 Randomization**

Once the investigator has determined that the subject and the procedure are eligible based on inclusion/exclusion criteria, the subject will be randomized in a 1:1 fashion to either robotic-assisted PCI or conventional manual PCI. Randomization is completed after the primary operator assesses the coronary lesion(s). Qualified subjects will be randomized to treatment using an Interactive Web-based Randomization System (IWRS). The IWRS will assign treatment arm and will be recorded in the CRF.

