## 5.7 IVUS assessment

The secondary endpoint for the clinical study will be the distance from the proximal stent edge to the true ostium as measured by IVUS following stent deployment. The aorto-ostium will be defined as the plane at which the coronary artery joined the aorta sinus. Protrusion of the stent beyond this plane (*protruding stent*) as well as the distance between this plane and the most proximal stent strut (*geographical miss*) will be measured. In the case of side branches (left anterior

descending or circumflex) the ostium will be defined as the plane between the side branch emerging point and the carina tip. Protrusion of the stent beyond this plane (*protruding stent*) as well as the distance between this plane and the most proximal stent strut (*geographical miss*) will be measured.

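### Ostium type (aorto-ostial or branch) is neither a randomisation stratum nor part of a prespecified primary analysis; if miss rates differ by type, a chance imbalance could move the result by a few points

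*Combined protocol and SAP*

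**What the plan says.** **Who enters.** Section 2.2 admits any coronary ostial lesion suitable for PCI. Section 2.3 removes only ostial left main disease and chronic total occlusion among lesion types. Aorto-ostial and branch lesions can therefore both be enrolled.

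**How the ostium is located.** Section 5.7 takes the junction of artery and aortic sinus as the plane for an aorto-ostial lesion. For the left anterior descending or circumflex, "the ostium will be defined as the plane between the side branch emerging point and the carina tip". Protrusion and geographical miss are then measured from whichever plane applies.

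**Randomisation.** Section 5.4 states that "the subject will be randomized in a 1:1 fashion to either robotic-assisted PCI or conventional manual PCI", through an IWRS, once the operator has assessed the lesion. No stratification, blocking or minimisation is described.

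**Statistics.** Section 3 is the whole statistical section. It gives "robotic PCI (n=33) or manual PCI (n=33) in a 1:1 ratio" and a sample size built on one pooled rate: "we estimated an overall incidence of geographic ostial miss of 50" per cent. It names no primary test, covariate or analysis by ostium type.

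**Rates by type.** The only one is in section 1.1, where "a retrospective analysis of 100 consecutive PCI of aorto-ostial lesions observed stent misplacement" in 54% of cases. There is no rate for branch ostia and no expected lesion mix.

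**The concern.** Ostium type is the one lesion characteristic for which the protocol itself changes the landmark that defines a miss, so it is a plausible prognostic factor for the primary endpoint. It is known before allocation, because angiography and lesion assessment come first. With 33 subjects per arm, simple 1:1 allocation can leave the arms with noticeably different lesion mixes. If one type is harder to cover, part of the observed arm difference would then reflect case mix and not the robot, and an unadjusted comparison could not separate the two. Section 5.5 already fixes one stent for all subjects to limit confounding, so the plan accepts the principle.

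**Working it through.** **Inputs from the documents.** 33 per arm; manual miss 50%; 70% relative reduction, so robotic miss 0.50 × 0.30 = 15% and a planned difference of 35 points; 80% power; 5% level (two-sided assumed, as sidedness is not stated).

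**Assumptions not in the documents.** Aorto-ostial share 30% to 50%; miss rates differing between types by 10 to 40 points; a miss treated as the complement of full coverage.

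**1. The plan's own figure.** Section 3 says that "66 subjects are required to have an 80% chance of detecting, as significant at the 5% level, a 70% decrease of geographic miss". Two-proportion formula, pooled rate 0.325:

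n = [1.96·√(2·0.325·0.675) + 0.842·√(0.50·0.50 + 0.15·0.85)]² / 0.35² = 26.9, so 27 per arm uncorrected.

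Continuity correction: (26.9/4)·[1 + √(1 + 4/(26.9·0.35))]² = 32.4, so 33 per arm and 66 in total. The stated figure reproduces exactly.

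**2. How often the mix is unbalanced.** With T aorto-ostial lesions among 66 subjects, the number A in one arm is hypergeometric. The imbalance in share is (2A − T)/33, with SD (2/33)·√[33·(T/66)·(1 − T/66)·(33/65)].

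- T = 20 (30%): SD 11.4 points; P(imbalance ≥ 20 points) = 5.9%.
- T = 33 (50%): SD 12.4 points; P(imbalance ≥ 20 points) = 13.9%.

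Treating the count in each arm as binomial gives 8.0% and 10.9%, inside the same range.

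**3. What an imbalance does to the estimate.** Shift = imbalance × gap in miss rate. At 20 points:

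- gap 10: 0.20 × 10 = 2 points
- gap 20: 4 points
- gap 40: 8 points

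This takes the same gap in both arms, that is, no treatment effect. If the robot cuts misses by 70% in each type, the robotic-arm gap is 0.30 of the manual one. With the imbalance split evenly around the mean, the multiplier is (1 + 0.30)/2 = 0.65, so the shift is 1.3 to 5.2 points.

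**4. Error rates (simulation, 200,000 trials per scenario, no true effect).** Averaged over all randomisations, the unadjusted uncorrected chi-square test rejects in 6.1% to 6.5% of trials when the types differ, against 6.4% when they do not. The excess over 5% comes from discreteness and not from imbalance. Mantel-Haenszel rejects in about 5%. Now take only trials in which the robotic arm has at least 20 points fewer high-miss lesions. At miss rates of 70%/30%, the unadjusted test falsely favours robotic in about 13% of them, against 3% when the types do not differ. Mantel-Haenszel stays near 5% two-sided in those trials.

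**5. Power at 33 per arm (same simulation, 70% reduction in each type).** Manual miss rates are aorto-ostial/branch.

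| Aorto-ostial share | Manual miss rates | Unstratified, unadjusted | Unstratified, Mantel-Haenszel | Stratified, Mantel-Haenszel |
|---|---|---|---|---|
| 50% | 50/50 | 88.8% | 87.8% | 88.4% |
| 50% | 60/40 | 88.8% | 88.3% | 88.9% |
| 50% | 70/30 | 88.8% | 90.4% | 90.8% |
| 30% | 50/50 | 88.9% | 87.8% | 88.3% |
| 30% | 60/40 | 84.7% | 83.8% | 84.2% |
| 30% | 70/30 | 79.7% | 81.1% | 82.0% |

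Power falls in the last two rows because the pooled manual rate falls below 50% (0.3×60 + 0.7×40 = 46%; 0.3×70 + 0.7×30 = 42%). Simulation error is about √(0.89·0.11/200,000) = 0.07 points.

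**The case against.** The strongest reply is that everything depends on miss rates differing by type, and the documents do not show that they do. If the 54% aorto-ostial figure and the pooled 50% are both taken at face value, the branch rate is 46% at a 50% share, or (50 − 0.3×54)/0.7 = 48.3% at a 30% share. The gap is then 5.7 to 8 points, and a 20-point imbalance shifts the result by only 1.1 to 1.6 points. At 54%/46%, stratified Mantel-Haenszel has 88.3% power against 88.7% unadjusted. This is only indicative: the 54% counts proximal and distal misplacement beyond 1 mm, and the 50% may simply be that figure rounded. It does stand as a reason to treat the 2 to 8 points as conditional.

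A reader might also infer any of the following, and the documents do not support them:

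- *Coverage is measured by two different rules.* Section 5.7 changes the anatomical plane and then takes the same two measurements from it. It is also introduced under the secondary distance endpoint, and bears on the primary only because it defines geographical miss, which sizes the trial.
- *The analysis deliberately ignores type.* Section 3 names no primary test, so the analysis is unspecified.
- *The false-positive rate is inflated, or 66 is wrong.* Averaged over randomisations the error rate is unaffected by imbalance, and 66 reproduces.

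Two practical objections also stand. Sections 5.4 and 5.6 allow for more than one lesion, so a subject could have both types. And ostium type is not listed as a CRF item, so it cannot be assumed to be collected.

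**Conclusion.** The gap is real and modest. Both ostium types are admitted, type is known before allocation, and neither the randomisation nor a prespecified analysis takes account of it. What is at stake is the estimate in the one trial that will be run: about 2 to 8 points against 35 for a 20-point imbalance, which is itself unlikely (6% to 14%) and equally likely to favour either arm. The upper end needs a 40-point gap between types and no treatment effect. The rate gap and the lesion mix are assumptions that the documents cannot settle. This is an inexpensive improvement and does not correct an error in the sample size or in the validity of the test.

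**What to change.** Before randomisation, designate one target ostial lesion per subject and record its type (aorto-ostial or branch) in the CRF. Define the branch category so that it covers any eligible branch ostium, since section 5.7 names only two vessels. Stratify the IWRS by that type. Add one sentence to section 3: the primary analysis is a Mantel-Haenszel risk difference and test stratified by ostium type, with results by type shown descriptively. If the IWRS is already live, make only the analysis change.

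**Cost.** No change to N; one IWRS factor (assuming the system supports it), one CRF item, a target-lesion rule, and a sentence that has to be written anyway because no primary test is named. If type turns out not to matter, power falls by about 0.5 points, or about 1 point for the analysis-only version. Two allocation lists in a single centre are a small operational burden, and short blocks would make allocation somewhat easier to predict.
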